### SECTION III: STUDY PROTOCOL

15. **Study Abstract:** Provide a brief, non-technical summary of the study, including study purpose and methods.

The purpose of this study is to quantify the impact of a formalized pain management education program on the outcome and experience of patients undergoing outpatient, upper extremity, orthopedic surgery. Outcome measures include the validated Quality of Recovery-15 patient survey and PROMIS survey (selected short forms evaluating pain and medication side effects), as well as measures of patient behavior (amount of pain medication used, number of calls/visits to a medical provider for pain-related concerns), pain levels (1-10 scale), reported side effects, and patient knowledge as measured on a follow-up questionnaire. It is the premise of this study that patient education regarding perioperative pain management could benefit patients in several ways:

- 1) empowering patients to make informed decisions regarding the pain medications and modalities they choose,
- 2) reducing the incidence and severity of pain medication related side effects or complications,
- 3) improving post-operative pain control,
- 4) improving patient satisfaction, and
- 5) reducing the use of narcotic.

Four hundred (400) adult patients undergoing elective outpatient, upper extremity, orthopedic surgeries will be recruited by the surgeon-investigators. Patients will be randomized to view one of two educational programs: 1) a 2-video series regarding post-operative pain management or 2) a video regarding wound care and activity. Randomization will be stratified based on initial narcotic prescription size, which has been shown to influence narcotic use, and baseline pain medication use.

These patients will be encouraged to review the video online in the week before surgery. An intake enrollment form will be completed by an investigator using demographic information available in the chart.

Participants in both arms will complete their Patient Education Study Diary daily, for 7 days following their surgery. There are two versions of this diary: the Wound Education Version asks patients to report daily pain medication use. The Pain Education Version does not include this section as patients in the pain management arm of the study record this information in their Recovery Diary.

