 The guidelines have been developed in conjunction with the upper extremity surgeons to reflect their current practice. The purpose of the guidelines is to reduce inadvertent variability, particularly when residents and other providers provide the post-operative prescription. Despite the guideline, the surgeon is still encouraged to provide the pain medication prescription he/she feels is most appropriate for the patient.

The Patient Education Study Diary includes a daily pain scale, the QoR-15 on day 2, the selected PROMIS short forms on day 3 and knowledge quiz on day 7. It also contains opportunity to report dressing changes, co-analgesic modalities (ice, elevation, etc), and possible medication side effects. There are daily questions regarding confidence, feeling in control, and satisfaction. The final day also has questions regarding how many times the videos were viewed, the number of contacts with a healthcare provider for pain and wound related issues, and concurrent use of other sedating substances (sleeping pills, alcohol, street drugs, other sedating medications). Patients in the control group (wound care) will also record all pain medications used each day along with any side effects of said medications. Participants in the intervention (pain management) group will record their pain medication use in the additional Recovery Medication Diary provided. The patient will return the diary at the first post-operative visit or by mail.

Patients may be contacted by phone within 7-10 days after the appointment if study materials are not complete. Information regarding the initial narcotic prescription, CPT procedure codes, concurrent NSAID prescription, and type of anaesthetic will be obtained from EPIC by chart review.

The patient will be contacted again by phone and/or mail 1 year after surgery (12-14 months) using the contact information available in EPIC to determine the self-reported prevalence of chronic pain and pain medication use (yes or no answers):

1. Do you have pain on a daily or weekly basis?
2. In the past year, have you taken prescription opioid (or narcotic) pain medication most days or most weeks?
3. In the past year, have any other pain medications (prescription or over the counter) most days or most weeks?

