Pre-operative education for post-discharge pain control has been promoted by AORN: "Effective communication between the patient, designated support person(s), and perioperative team members enhances the patient's capacity for medication self-management after discharge."

Specific communication about pain has been shown to correlate strongly with patient satisfaction. Five dimensions have been identified as impacting on patient satisfaction: information provision; physical comfort/discomfort; emotional support; involvement in care; and privacy. In an inpatient setting, higher self-report of pain was associated with lower levels of satisfaction. Patients reporting adequate teaching rated a higher satisfaction score (4.46) than patients reporting inadequate teaching.

Patient education in the outpatient setting is essential in allowing the active participation of the patient in their own health care, and could reasonably increase patient safety in a way similar to in-hospital programs that have been shown to reduce medication errors. The effect of pre-operative patient education on decreasing narcotic use and improving pain control has been demonstrated on one study of 135 patients who were randomized to receive educational intervention vs no education.

Recent interest in the over-prescription of narcotic pain medication after outpatient surgery has led to several studies which suggest standardized protocols for prescription sizes. The Hand Section of the Department of Orthopedics at Carilion clinic has recently submitted for publication a manuscript showing the effect of initial prescription size on narcotic use in this setting. We are also participating in a multi-center international trial of narcotic vs. non-narcotic analgesics for pain control after carpal tunnel surgery. Investigating the role of patient education in post-operative pain management is an extension of this line of research.

This study will be a prospective, randomized, placebo-controlled experimental study investigating the effect of a formalized patient education program (videos and recovery diary handout) on patient experience and outcome after outpatient orthopedic upper extremity surgery, using both validated and non-validated outcome measures.

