17. **Objectives:** State the research hypothesis or the question that the research will answer. List the research objectives and expected outcomes. **A primary outcome or objective must be identified.** After the statement of the primary objective, secondary objectives may be listed. Objectives should be simple and specific.

Hypothesis: Patient experience and outcome after outpatient upper extremity orthopedic surgery can be improved by a formalized education program (video and handout) regarding post-operative pain management.

Primary outcome:

1. QoR-15 scores (post-operative day "POD" 2),
  - a. 15-question validated outcome measurement tool used in the setting of outpatient surgery which takes about 2.5 minutes to complete and includes pain as one of its outcome domains

Secondary Outcomes:

2. PROMIS short forms administered on POD 3 – (GI belly pain 5a, GI nausea and vomiting 4a, Pain Intensity 3a, Pain Interference 4a, Sleep Disturbance 4a, Cognitive Function 4a)
3. number of narcotic pills used – 7 days,
4. daily pain level (by 0-10 rating scale) – 7 days,
5. patient-reported satisfaction and feeling of control (4 point rating scale)
6. number of pain-related calls/visits to a healthcare provider
7. use of non-narcotic adjunct pain relief medication and modalities
8. incidence of high risk activities (combining narcotics with muscle relaxants/sedatives/alcohol, etc.; combining prn NSAIDs with regularly dosed prescription NSAIDs, exceeding daily recommended doses)
9. incidence of side effects and adverse events,
10. demonstrated patient knowledge as measured by score on the follow-up quiz, and
11. prevalence of chronic opioid use.

Positive improvements in some or all of these measurements are expected with this patient education intervention. The Quality of Recovery-15 survey is a 15-question validated outcome measurement tool used in the setting of outpatient surgery which takes about 2.5 minutes to complete and includes pain as one of its outcome domains

18. **Study Design:** Give a description of the research design including use of placebo, randomization and an explanation of what is experimental. Include type of study: descriptive, retrospective, cross-sectional, longitudinal, prospective observational, pilot, experimental (controlled or non-controlled) or pilot.

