    - a. A series of two 6-minute videos. The first video, Managing Pain after Outpatient Surgery, Part 1, discusses a tiered approach to pain management, including rest, ice, elevation, distraction, and medication. Three classes of pain medication commonly used after surgery, including nonsteroidal anti-inflammatories, acetaminophen, and opioids, are discussed, including the role of each medication and the risks and side effects. Naloxone, an antidote to opioid medication for emergency use, is introduced. The second video, Managing Pain after Outpatient Orthopedic Surgery, Part 2, instructs the patient on how to make a Pain Plan with regard to post-operative pain medication, including the use of over the counter pain medications and a medication diary. (12 minutes)
    - b. Recovery Medication Diary (1-7 minutes, daily, for 7 days)
  - 2) Wound Care Education (Control)
    - a. A single video, Caring for Your Closed Wound, discusses the types of sutures that are used to close surgical wounds, the specifics of wound care and dressing changes, swelling management, restriction of physical activity, scarring of the surgical site and

methods to reduce scarring, and guidance on when to call their physician if they suspect something to be wrong following their procedure. (6 minutes)

Patients are encouraged to view the video(s) in the examining room of the clinic before departure on a tablet device. Patients who elect to watch the video will be offered a small bottle of water, due to the extended visit and as a “fidget” to aid in attention. The videos will also be “assigned” to the patient in MyChart through the GetWellNetwork, and also available for viewing online on the Carilion channel on YouTube.

5. Patient packet dissemination (< 1 minute)

All patients in the study will receive an enrollment package with includes a copy of the consent form, video web address, and Patient Education Diary (experimental or placebo version). Patients in the Pain Control Video group will also receive a Recovery Diary corresponding to the video.

6. Data Collection (1-7 minutes daily for 7 days)

Patients are invited to view the video on the GetWellNetwork through MyChart and on YouTube. Viewing will be tracked by patient report, and by tracking views on the GetWellNetwork. (Viewing by patient report will be used in statistical analysis, comparison to GetWellNetwork data will be exploratory.)

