Participants in both arms will complete a Patient Education Study Diary daily for 7 days following their surgery. Patients in the control group (wound care) will also record all pain medications used each day along with any side effects of the medications. Participants in the intervention (pain management) group will record their pain medication use in the additional Recovery Medication Diary provided.

Patients will receive a phone call from either an investigator or the study coordinator on Day 1-3 and Day 5-7 to remind them to complete their diaries and to answer any questions the patient may have (see attached script).

Patients will return their diaries at their first post-operative visit. If they do not bring the diaries to the post-operative visit, they will be given a self-addressed, stamped envelope to facilitate return. Patients will be contacted by phone (with permission) <10 days and 14-21 days following surgery and again 21-28 days after surgery if they have not returned their study materials as a reminder.

The Follow-up Questionnaire will be completed at the 1st post-operative visit, or by phone within 7-10 days of that appointment. The patient will be contacted again by phone and/or mail 1 year after surgery

(12-14 months) using the contact information available in EPIC to determine the self-reported prevalence of chronic pain and pain medication use:

1. Do you have pain on a daily or weekly basis?
2. In the past year, have you taken prescription opioid (or narcotic) pain medication most days or most weeks?
3. In the past year, have you used pain medications (prescription or over the counter) most days or most weeks? (list medications used on a daily or weekly basis for pain)

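### Pain medication use is logged in a different booklet in each arm, and the intervention arm's booklet is part of the intervention, so recorded pill use may differ between arms for reasons unrelated to consumption

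*Protocol*

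**What the plan says.** Item 15 (Study Abstract) describes two versions of the Patient Education Study Diary. The wound-care (control) version has a daily section for pain medication. For the pain-management version: "The Pain Education Version does not include this section as patients in the pain management arm of the study record this information" in the Recovery Diary. Items 15 and 20 (Methodology, Data Collection) both state the split: "Participants in the intervention (pain management) group will record their pain medication use in the additional Recovery Medication Diary provided".

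The Recovery Diary is treated as part of the intervention in three places:

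- Item 16 (Background) defines the programme as the videos plus the recovery diary handout.
- Item 20, step 4, lists the Recovery Medication Diary as component b of Pain Management Education (Intervention).
- The section on how the study differs from usual care names the video series and the Recovery Diary as what the intervention group receives in addition.

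The second intervention video instructs patients on a pain plan, "including the use of over the counter pain medications and a medication diary". As described, the control video covers wound care and activity and has no such content.

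On other sources, item 15 says that the initial narcotic prescription, procedure codes, "concurrent NSAID prescription, and type of anaesthetic will be obtained from EPIC by chart review". Item 21 pools chart review, physician and patient reporting, and diaries or surveys as sources for all data. It does not tie any of them to a count of pills taken.

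**The concern.** Arm assignment determines both the form on which medication is recorded and whether the patient has been taught to keep such a record. A between-arm difference in recorded pills could then come from a difference in consumption, a difference in recording, or both, and no analysis of the returned booklets can separate them. The intervention arm also has a second booklet to complete and return, so missing medication data could differ by arm even if the two layouts were identical.

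Reduced narcotic use is one of the five expected benefits in item 15, and 7-day pill count is outcome 3 in item 17. Use of non-narcotic medication (the drug part of outcome 7) has the same weakness. Two parts of the high-risk-activity outcome may share it: "combining prn NSAIDs with regularly dosed prescription NSAIDs, exceeding daily recommended doses". The prescribed-NSAID half of the first part comes from the chart in both arms, but as-needed use and dose totals would need a patient log. The outcome list in item 21 omits high-risk activities, so their source is not stated. Side-effect reporting may also be touched: both study diaries allow it, but control patients additionally record side effects alongside their medications.

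**Working it through.** **Which outcomes depend on the split record**

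| Outcome | Control arm source | Intervention arm source | Same instrument? |
|---|---|---|---|
| QoR-15, PROMIS, daily pain, non-drug modalities, sedating substances | Study diary | Study diary | Yes |
| Narcotic pills, 7 days | Study diary section | Recovery Medication Diary | No |
| Non-narcotic pain medication | Study diary section | Recovery Medication Diary | No |
| Prescribed NSAID | Chart | Chart | Yes |
| As-needed NSAID use, dose exceedance | Not stated; would need a log | Not stated; would need a log | Probably not |

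**The plan's own figure.** The only design calculation (item 22) is for QoR-15: difference 8, SD 25, alpha 0.05, power 0.8. With two-sided alpha, n = 2 × (1.960 + 0.842)² × (25/8)² = 153.3, so 154 per group, and 154/0.80 = 192.5, so 193, rounded up to 200. This reproduces the protocol and does not depend on the medication record.

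**What a capture gap would do.** The protocol gives no mean, SD or recording completeness for pills, so the size of any bias cannot be computed. The following is an illustration.

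- From the protocol: 200 per arm less 20% attrition = 160 evaluable; 154 per arm as an alternative.
- Assumed: no true difference; one booklet captures a fraction g fewer pills than the other; SD/mean = 0.75, 1.0 or 1.5; two-sided t-test at 0.05.
- Spurious difference = g × mean. Noncentrality = (g ÷ SD/mean) × √(n/2), with 2n − 2 degrees of freedom.
- Example: g = 0.10, SD/mean = 1.0, n = 160 gives 0.10 × √80 = 0.894. The chance of p<0.05 is then 0.145.

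Chance of p<0.05 with no true effect, n = 160 per arm:

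| Gap g | SD/mean 0.75 | 1.0 | 1.5 |
|---|---|---|---|
| 1% | 0.052 | 0.051 | 0.050 |
| 3% | 0.065 | 0.058 | 0.054 |
| 5% | 0.091 | 0.073 | 0.060 |
| 10% | 0.221 | 0.145 | 0.091 |

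With n = 154 the 5% row becomes 0.090, 0.072, 0.060 and the 10% row 0.215, 0.141, 0.090.

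The false-positive rate doubles to 0.10 at gaps of 5.5%, 7.3% and 11.0% (n = 160) or 5.6%, 7.5% and 11.2% (n = 154).

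As a check on the normal model, gamma-distributed counts (20,000 simulated trials, t-test, n = 160) gave 0.094, 0.071, 0.059 at a 5% gap and 0.235, 0.154, 0.092 at 10%.

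**The case against.** **Mitigation already in the plan.** Both arms get reminder calls on days 1-3 and 5-7, calls about incomplete or unreturned materials, and stamped envelopes. These reduce incomplete and unreturned booklets in both arms. They do not give the arms a common instrument or undo the teaching of diary use in one of them.

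**Unseen materials.** The diary pages, the call script and the Follow-up Questionnaire are not shown. The medication pages may ask for the same content, and the questionnaire might ask about pills. This stands as a limit: the point concerns what the protocol describes. Even with matching layouts, one arm's outcome record would be part of its treatment and sit in a separate booklet.

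**Magnitude.** Gap and SD/mean are both assumed, small gaps are nearly harmless, and the plan names a mixed-model ANOVA rather than a t-test. All true, which is why the table includes the small gaps. A different model would change the rates but would not remove a bias built into the recorded values.

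**A reasoned trade-off.** Omitting the section avoids double entry, and item 22 aims to keep the diary short and simple. Patients could also copy from the Recovery Diary, so a common item would not equalise recall support. This stands, and it makes the remedy partial. It still equalises wording, format and data source, and the control version already carries such a section.

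**Existing check.** Item 21 lists the reported frequency of noting dose times. It bears on recording behaviour and could support a partial check, but it does not yield a common pill count.

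**Conclusion.** The concern holds as a design weakness limited to secondary outcomes. Followed exactly, the plan measures narcotic pill count and non-narcotic medication use with an arm-specific instrument that, in one arm, is also part of the treatment. Analysis cannot repair this afterwards. The log-based parts of high-risk activities, and possibly side-effect reporting, may be affected too. QoR-15, PROMIS, non-drug modalities, the sedating-substances question and the sample size are not.

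The size and direction of any bias are unknown. Under the stated assumptions, a capture gap of roughly 5.5% to 11% would double the false-positive rate for pill count, while a gap of 1-3% would hardly move it. The documents do not show that a gap exists. It should be fixed because the change is cheap and the outcome bears directly on one of the stated aims. Confidence is medium, because the booklets themselves were not available.

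**What to change.** Put one identical, short daily medication item (drug, tablet strength, number taken) in both versions of the Patient Education Study Diary. Name it in items 20 and 21 as the sole source for narcotic pill count, non-narcotic medication use and any high-risk item that relies on a log. Keep the Recovery Medication Diary as an intervention aid that is not an outcome source.

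Cost: one diary version is reprinted, and intervention patients make a brief duplicate entry for 7 days in the booklet that also carries QoR-15, which works against the aim of a minimal diary. Copying from the Recovery Diary remains possible, so the difference in recall support should be acknowledged when the medication results are interpreted.

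### Secondary outcome 9 (side effects) is not collected comparably in the two arms: the teaching and the diary prompts both differ by arm, so a between-arm difference cannot be read as a difference in symptoms

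*Protocol*

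**What the plan says.** Secondary outcome 9 in item 17 is the "incidence of side effects and adverse events". It bears on one of the five benefits listed in item 15, namely "reducing the incidence and severity of pain medication related side effects or complications".

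The instrument described for side effects is the Patient Education Study Diary, kept for seven days. Item 15 says of it: "It also contains opportunity to report dressing changes, co-analgesic modalities (ice, elevation, etc), and possible medication side effects".

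The arms differ in two relevant ways.

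- **Teaching.** Item 20, step 4, says the pain videos cover three drug classes, "including the role of each medication and the risks and side effects". The control video "discusses the types of sutures that are used to close surgical wounds, the specifics of wound care and dressing changes", and also swelling, activity, scarring and when to call. No medication content is described for it.
- **Recording.** Item 15, repeated in item 20, step 6, says of controls: "Patients in the control group (wound care) will also record all pain medications used each day along with any side effects of said medications". Of the other arm it says: "Participants in the intervention (pain management) group will record their pain medication use in the additional Recovery Medication Diary provided". Side effects are not mentioned for that second diary.

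The PROMIS belly pain, nausea and vomiting, sleep and cognition forms are given in both arms before the video (item 20, step 3) and on post-operative day 3 (item 17). They are secondary outcome 2.

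**The concern.** To be counted, a symptom has to occur, be noticed, be linked by the patient to a medication, and be written down. Randomisation is meant to change the first step. Here it may change the later ones too. Patients taught what the drugs can do may recognise and attribute more of the same symptoms. Controls, prompted each day for side effects next to their medication entries, may write more down for a different reason.

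The count in each arm then mixes symptoms with reporting behaviour. A real reduction could be hidden, or a difference in either direction could appear with no difference in symptoms. Analysis cannot repair this, because a symptom that was not reported leaves no record.

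**Working it through.** **The plan's own figures.** The protocol gives no figure for outcome 9. Its sample size concerns QoR-15 and is used here only for the number per arm. With a difference of 8, SD 25, two-sided 5% and 80% power: n = 2 × (25 × (1.960 + 0.842) / 8)² = 153.3, so 154 per group, as stated. Allowing for 20% attrition, 154 / 0.80 = 192.5, so 193, rounded by the protocol to 200. Both figures reproduce.

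**Model.** Reported incidence = true incidence × probability that the patient reports the symptom as a side effect. The reported risk ratio is therefore the true risk ratio × (reporting probability in the pain arm / that in the control arm). The documents give none of these quantities; every rate below is an assumption.

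**No true difference, reporting differs.** With reported proportions p₁ and p₂, their mean p̄ and n = 154 per arm, the chance of p < 0.05 is approximately Φ{(|p₁ − p₂| − 1.96 √[2p̄(1 − p̄)/n]) / √[(p₁(1 − p₁) + p₂(1 − p₂))/n]}.

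| True incidence, both arms | Reported where reporting is 0.6 | Reported where reporting is 0.8 | Gap (points) | Chance of p < 0.05 |
|---|---|---|---|---|
| 20% | 12% | 16% | 4 | 0.171 |
| 30% | 18% | 24% | 6 | 0.252 |
| 40% | 24% | 32% | 8 | 0.345 |
| 50% | 30% | 40% | 10 | 0.452 |

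Worked for the last row: p̄ = 0.35; √(0.455/154) = 0.0544; √(0.45/154) = 0.0541; (0.10 − 1.96 × 0.0544)/0.0541 = −0.12; Φ(−0.12) ≈ 0.45.

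The table reads both ways:

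- If teaching dominates (pain arm 0.8, control 0.6), the gap is a false excess in the pain arm.
- If the control-only prompt dominates (control 0.8, pain arm 0.6), it is a false reduction of the same size.
- If the two cancel (for example 0.7 and 0.7), there is no distortion.
- A smaller gap, 0.6 against 0.7, gives 2 to 5 points and a rejection chance of 0.075 to 0.153.

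**A true fall from 40% to 30% in the pain arm.**

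- Control 0.6, pain arm 0.8: 0.40 × 0.6 = 24% and 0.30 × 0.8 = 24%. The fall disappears.
- Control 0.8, pain arm 0.6: 0.40 × 0.8 = 32% and 0.30 × 0.6 = 18%. The fall of 10 points appears as 14.

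**The case against.** The strongest reply is that the diary page is not among the documents. The sentence about it comes from a brief lay abstract, and the entry might already be a list of named symptoms. That stands. A reader might infer an open free-text entry that forces the patient to judge cause, but the protocol does not say so. What remains without the page is the wording about medication side effects and the prompt described for controls only.

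Second, item 15 itself describes the PROMIS forms as evaluating medication side effects. They do not ask about cause, are identical in both arms and have a pre-video baseline. This also stands, so the stated benefit does not rest on outcome 9 alone. But the forms cover selected domains, with one post-operative assessment on day 3. They do not give a seven-day incidence and do not define outcome 9.

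Third, a reader might infer that controls hear nothing about side effects. The documents do not support that: both arms keep the nurse's discharge medication review and written instructions (end of item 20). Whether those cover side effects is not stated, and item 16 says this teaching comes when retention may be impaired. The contrast is between the study's two education programmes.

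Fourth, a checklist counts symptoms from any cause, and taught patients may still tick it more readily. Both points are fair: the change reduces the bias but does not abolish it.

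**Conclusion.** The concern holds as a problem of comparability. Outcome 9 as described combines symptoms with reporting, and two features that affect reporting differ by arm.

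A reader might go further and conclude that the pain arm will show inflated side effects. The documents do not support a direction, because the control-only prompt may push the other way. They do not support a size either. The 4 to 10 points, and rejection chances of 17% to 45% in place of 5%, follow from assumed incidences of 20% to 50% and assumed reporting of 0.6 against 0.8, with either arm the higher.

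The conclusion assumes that the diary reads as item 15 describes it and that the Recovery Medication Diary has no matching side-effect prompt. It concerns the side-effect part of one of ten listed secondary outcomes. QoR-15 and the sample size are not touched.

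**What to change.** 1. In both diary versions, use one identical daily checklist of named symptoms (present or absent, with severity) that asks nothing about cause, plus a free-text line for anything else.
2. Remove the side-effect prompt from the control arm's medication log, or put the same prompt in the Recovery Medication Diary.
3. Define the side-effect part of outcome 9 from the common checklist, for example any listed symptom over the seven diary days.
4. Read it alongside the PROMIS gastrointestinal, sleep and cognition scores at baseline and day 3.

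If the diary already carries such a checklist, only step 2 changes the forms.

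The cost is a reworded page in each diary version and one matched or deleted prompt, made before the diaries are printed. The price in interpretation is that symptoms unrelated to medication are counted as well, which dilutes a drug-specific effect, and that some difference in awareness between the arms may remain.
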